PROTOCOL OLIGOPELVIS 1_GETUG P07

A) CLINICAL TRIAL IDENTIFICATION

STUDY TITLE	Multicentric phase II study of high-dose radiotherapy and hormone therapy in oligometastatic relapses of the pelvic lymph nodes of prostate cancer
SHORT TITLE	OLIGOPELVIS 1_GETUGP 07
INVESTIGATOR COORDINATOR	Pr [name]
ID-RCB	2014-A00138-39
REF ANSM	140494B-12 AUTORISATION 13/06/14
ETHICS COMMITTEE NAME	CPP OUEST-IV
REF ETHICS COMMITTEE	19/14 SESSION OF 13/05/14
N° CLINICAL TRIAL.GOV	NCT02274779

B) STUDY BACKGROUND

There is a growing body of evidence reporting the existence of a subset of prostate cancer patients who, at relapse, present with a limited number of metastases (fewer than five lesions). This oligometastatic state has also been identified in other tumor types, such as melanoma, soft tissue sarcoma, liver, lung, and breast cancers, and has led to a shift in management toward more aggressive local treatments, including surgical resection.

Positron Emission Tomography–Computed Tomography (PET-CT), using tracers such as choline or acetate, has proven to be a reliable tool for detecting oligometastatic disease following biochemical recurrence in prostate cancer. For patients in this setting, an intensified therapeutic approach—combining androgen deprivation therapy (ADT) with high-dose radiation therapy directed at PET-CT-detected lesions—may be proposed.

This strategy has the potential to prolong the interval between successive courses of ADT or, in selected patients with a limited metastatic burden, may even offer the possibility of cure.

In this study, the investigators aim to evaluate the 2-year biochemical or clinical relapse-free survival of prostate cancer patients with 1 to 5 oligometastases treated concomitantly with high-dose conformal radiation therapy and LH-RH agonists.

C) STUDY INFORMATION

INDICATION	Oligometastatic lymph nodes pelvic prostate cancer patients	
METHODOLOGY	Non randomized, prospective, national multicentre, phase II	
Primary Objective and Endpoint		
Primary objective	Endpoint	Evaluation time
The primary objective is to evaluate the biochemical or clinical relapse-free survival at 2 years.	The primary endpoint is the 2-year relapse-free survival probability. Biochemical or clinical relapse is defined as: 
 • A PSA level higher than the pre-treatment PSA value, confirmed by 	2 years

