	
two consecutive increases measured in the same laboratory; and/or
 
 An increase in the number of metastatic sites on follow-up imaging assessments. 	
SECONDARY OBJECTIVES AND ENDPOINTS		
Secondary objectives	Endpoints	Evaluation time
a) Biochemical relapse-free survival	
A PSA > 0.2 ng/mL after the post-treatment nadir (or PSA > nadir + 0.2 ng/mL if nadir > 0.2 ng/mL).
 
For patients without a history of prostatectomy, biochemical recurrence is defined by:
 
 A PSA > pre-treatment nadir AND A PSA > 0.2 ng/mL after the post-treatment nadir 	2 years
b) Time to resumption of hormone therapy	Resumption of hormone therapy	5 years
c) Time to initiation of any subsequent treatment	Resumption of any treatment	5 years
d) Assessment of toxicity (acute toxicity assessed 1 month after the end of radiotherapy, and late toxicity assessed at 2 years), with particular attention to gastrointestinal events	NCI-CTC-AE v4.0 scale	5 years
e) Site of relapse: within the irradiated field or at distant (non-irradiated) sites	
At least one morphological imaging (depending on recurrence location and center practice):
 
 Abdominopelvic CT scan and/or Pelvic MRI and/or Bone scintigraphy and/or FCH-PET (post-treatment PET will be optional). 	5 years
f) Overall survival	Overall survival	5 years
g) Quality of life	QLQ-C30 + QLQ-PR25	5 years
h) Optional ancillary biological study: validation of a novel mutational signature in patients with oligometastatic prostate cancer treated with radiotherapy		
INCLUSION CRITERIA	
 Histologically proven adenocarcinoma of the prostate Patients aged 18 years or more PS 0-1 	

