DESCRIPTION OF ANALYSIS SETS	
The statistical analysis will be conducted with SAS 9.4 (Institute Inc., Cary, NC, USA), Stata 13.1 Special Edition (StataCorp LP, College Station, Texas, USA). For all analyses, a p-value of less than 0.05 was considered as statistically significant. All reported p-values are two sided.
 
Description of analysis sets Data from all evaluable patients will be analyzed.
 
Descriptive statistics A descriptive analysis of the patients included will be carried out. This analysis will include point estimates, numbers and percentages for qualitative variables, and mean, standard deviation, median, quantiles and range for quantitative variables.
 
Analysis of safety endpoints If a patient presented the same toxic event several times, only the higher grade event was analyzed.
 
Analysis of survival endpoints The different survival endpoints were analyzed are defined as follows:
 
Progression-free survival (PFS): time from randomization until biochemical-clinical failure or death from any cause. The definition of a biochemical-clinical failure is detailed in section 8.5.1. Overall survival (OS): time from randomization until death from any cause.
 
Patients for whom the event will not occur during the follow-up period will be censored at their last follow-up date. For PFS and OS, the determination of survival curves will be performed by means of Kaplan-Meier method.
 
Analysis of quality of life scoring Quality of life scores were compared between baseline and 6 months, and between baseline and 12 months using a Wilcoxon signed test for matched pairs. A Benjamini-Hochberg procedure was applied to control for false discovery rate. Quality of life differences were considered as clinically relevant when greater than 10.
 
Statistical criteria for stopping the study An analysis of acute toxicity persisting at one month after radiotherapy will be performed after the inclusion of the 20th patient to ensure that the toxicity of the irradiation protocol is not higher than expected. If, among the first 20 patients, 10 or more patients present with grade 2 toxicity, we can state that the rate of grade 2 complications is greater than the reference norm of 30 % ($p = 0.048$). In this case the Data Safety Monitoring Board (DSMB) will meet to analyze the toxicity and decide whether to continue the study. If, among the first 20 patients, 2 or more patients present with grade 3 toxicity, we can state that the rate of grade 3 complications is above the reference norm of 2 %

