
(p = 0.059). In this case the DSMB will meet to analyze the toxicity and decide whether to continue the study.

G) STUDY CALENDAR

DURATION OF INCLUSION PERIOD	24 months
TREATMENT DURATION	ADT + IG-IMRT: 6 months of ADT / 6 to 7 weeks (30 fractions) of IG-IMRT
POST TREATMENT FOLLOW UP	10 years
PRIMARY ENDPOINT ANALYSIS EXPECTED DURATION	2 years
STUDY COMPLETION DURATION (INCLUDING FU PERIOD)	12,5 years

SCHEDULE OF STUDY ASSESSMENTS

Visits	Inclusion Max 2 months prior to RT day 1	Treatment period	follow-up		
			M1 1 month after end of RT	Before progression Every 6 months during 2 years	After progression Every 6 months until death
Inclusion/exclusion criteria	X				
Signed consent form	X				
Inclusion (max 2 months prior to RT)	X				
FCH PET	X (a)				X (b)
Physical examination with PS	X	X (d)	X	X	X
Prior history, tumor characteristics	X				
Blood Pressure	X	X (d)	X	X	
Acute toxicity during ADT and RT (f)		X (d)	X		
Late toxicity (f)				X	
QLQ-C30 et QLQ-PR25	X		X	X	
PSA	X		X (f)	X (f)	X (f)
Testosterone	X (g)		X	X	X
ADT (c) + RT		X			

(a) maximum 3 months prior to initiation of ADT

(b) at progression

(c) 6 months treatment starting on RT day 1 or maximum 3 months prior to RT

(d) once per week during RT

(e) biochemical progression = PSA higher than inclusion PSA with 2 successive rises in the same laboratory

(f) NCI-CTCAE v4.0

(g) 28 days prior to ADT

STUDY DIAGRAM

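### PFS is censored at a last follow-up date that need not carry a PSA or imaging assessment, so the 2-year Kaplan-Meier estimate can be biased upward

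*Combined protocol and SAP*

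**What the plan says.** Section C gives the primary endpoint: "The primary endpoint is the 2-year relapse-free survival probability". Relapse has two components. One is a PSA criterion, which a note to the schedule in section G restates as "biochemical progression = PSA higher than inclusion PSA with 2 successive rises in the same laboratory". The other is an imaging criterion: "An increase in the number of metastatic sites on follow-up imaging assessments".

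Under the survival endpoints in section F, PFS is "time from randomization until biochemical-clinical failure or death from any cause". The estimator is stated for both endpoints at once: "For PFS and OS, the determination of survival curves will be performed by means of Kaplan-Meier method". So is the censoring rule: "Patients for whom the event will not occur during the follow-up period will be censored at their last follow-up date". The plan does not define the last follow-up date, does not tie it to a disease assessment, and has no rule for missed assessments.

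The schedule in section G has a column headed "Before progression Every 6 months during 2 years", in which PSA is marked. FCH PET is marked only at inclusion and at progression. Post-treatment follow-up is given as 10 years.

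The formal test is in the sample size part of section F. It rejects a 2-year rate of 50% or less if at least 39 of 63 evaluable patients are relapse-free at 24 months. Evaluable is not defined.

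**The concern.** Any contact shows that a patient is alive, so the last follow-up date is a sound censoring date for OS. It does not show that a patient is free of relapse. If the last PSA was at month 12 and the last contact at month 24, a literal application of the rule keeps the patient at risk and relapse-free for 12 months in which no relapse could have been recorded.

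The plan leaves room for the two dates to separate:

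- Visits also carry physical examination, toxicity and quality of life, so a visit can take place without a usable PSA.
- A PSA from a different laboratory does not meet the same-laboratory condition.
- As the schedule reads, PSA before progression is planned for 2 years, while follow-up runs to 10. Someone who misses the month-18 and month-24 PSA but is seen later stays at risk across the 24-month time point.

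The error can only run upward, and a single-arm trial has no control group to share it. At stake is the reported 2-year PFS figure.

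**Working it through.** **1. The plan's own figures.** Inputs from section F: null rate 50%, target rate 70%, n = 63, cut-off 39, 10% loss.

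- Fleming sample size by normal approximation, one-sided 5% error and 95% power: 62.1, rounded up to 63.
- Recruitment: 63 / 0.90 = 70.
- Exact error: P(X ≥ 39 | 63, 0.5) = 3.85%.
- Exact power: P(X ≥ 39 | 63, 0.7) = 93.56%, against 93.5% stated.

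The design reproduces. None of these figures uses a censoring date.

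**2. Effect on the Kaplan-Meier estimate.** The documents give no gap between last PSA and last contact, so the following are assumptions:

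- relapse times are exponential and relapse is detected at 6-monthly visits;
- 10% of patients stop having PSA, with the last one at month 0, 6, 12 or 18 with equal chance;
- contact without PSA then continues for g months.

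Simulation with 200,000 patients per scenario gives the excess of the 24-month estimate under last-contact censoring over last-PSA censoring:

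| g (months) | True rate 50% | True rate 70% |
|---|---|---|
| 0 or 3 | 0.0 points | 0.0 points |
| 6 | +1.0 | +0.7 |
| 12 | +1.9 | +1.3 |
| 24 (contact past month 24) | +2.8 | +1.8 |

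The zero at 3 months reflects the 6-month detection grid. With off-schedule visits it would be small rather than exactly zero.

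The last row can be checked by hand. If everyone without an event stays in contact to month 24, the excess is f × [mean S(last PSA) − S(24)].

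- S(24) = 0.5: S at 0, 6, 12 and 18 months is 1, 0.841, 0.707 and 0.595. The differences from 0.5 sum to 1.143, with mean 0.286. Times 0.10, this is 2.9 points.
- S(24) = 0.7: the values are 1, 0.915, 0.837 and 0.765. The differences from 0.7 sum to 0.717, with mean 0.179. Times 0.10, this is 1.8 points.

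Both agree with the simulation. Losing 30% of patients to PSA, which is beyond the planned loss, would give +2.2 to +3.3 points at g = 6 and +5.4 to +8.6 at g = 24.

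**3. The 39 of 63 count.** Censoring does not enter it. It would be disturbed only by a separate decision to count m unassessed patients as relapse-free. The error is then P(X ≥ 39 − m | 63 − m, 0.5):

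- m = 0: 3.85%
- m = 1: 4.90%
- m = 2: 6.19%
- m = 3: 7.75%

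**The case against.** The strongest reply is that the two dates may be the same. In the schedule, follow-up is the heading over three columns, and PSA is marked in all three. If the last follow-up date means the last protocol visit, it is normally a PSA date and the bias is zero. This stands. A reader might infer from the censoring sentence that the 2-year estimate is inflated. The documents do not support that, because they neither define the date nor give a gap. They support only that it can be inflated for patients who depart from the schedule, and those are the patients for whom a censoring rule is written.

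A reader might also carry the bias into the formal test. With half of patients relapsed at 24 months and 10% (20%) of patients last tested at month 12 but in contact at month 24, the excess is 0.10 (0.20) × (0.707 − 0.5) = 2.1 (4.1) points. Adding that to the 50% null rate would raise the error to 7.5% (13.3%). The arithmetic is right, but the inference does not follow: the test is a count, not a Kaplan-Meier estimate. The allowance from 63 to 70 also suggests that the 63 are meant to be patients who reach the 24-month evaluation. Since evaluable is undefined, a narrower point remains: nothing in the plan requires a month-24 PSA.

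The size is also open to challenge. The plan's 10% is loss to follow-up, and patients who are truly lost have no later contact to credit. The 10% used above is borrowed from that figure, and the resulting 1 to 3 points are small beside the 20-point contrast between 50% and 70%.

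**Conclusion.** The concern holds as a gap in the censoring rule. Section F uses for PFS a date that is right for OS and does not require it to carry a disease assessment. Followed literally, the rule credits unassessed time as relapse-free and can push the 2-year Kaplan-Meier PFS estimate upward. The range is 0 points if follow-up dates are PSA dates, and about 1 to 3 points if 10% of patients lose PSA and have 6 to 24 months of further contact. That range rests on exponential relapse, 6-monthly detection and an assumed gap. The 39 of 63 rule, its 3.85% error and its power are unaffected by censoring. They would change only if patients without a month-24 assessment were counted as relapse-free, and two such patients would be enough to take the error above 5%.

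**What to change.** In the survival endpoints part of section F:

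- For PFS and every relapse endpoint, censor patients without an event at the date of their last PSA, or of imaging if done. No routine imaging is scheduled before progression, so this will usually be the PSA date.
- Keep the last date known alive for OS only.
- State that a patient counted as relapse-free among the 63 must have a PSA at or near month 24, with the window given, and define evaluable accordingly.
- Add a sensitivity analysis for missed assessments, including a last PSA that was a first, unconfirmed rise, and for deaths after a PSA gap, since PFS counts death from any cause.

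The cost is a few sentences. PSA is already scheduled, and the sample size, cut-off, error and power do not change. Intervals will be slightly wider and the estimate slightly lower. Censoring at the last PSA is unbiased only if PSA is missed for reasons unrelated to relapse; if patients skip it because they are deteriorating, this rule is informative too. That is why the sensitivity analysis is needed.

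### The single 20-patient toxicity look can flag only large excesses, so it cannot ensure that toxicity is not higher than expected

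*Combined protocol and SAP*

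**What the plan says.** Section F, under Statistical criteria for stopping the study, provides one formal look. It concerns acute toxicity still present one month after radiotherapy, and its timing and purpose are given as "after the inclusion of the 20th patient to ensure that the toxicity of the irradiation protocol is not higher than expected".

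There are two triggers in the first 20 patients:

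- **Grade 2:** if "10 or more patients present with grade 2 toxicity", the plan concludes that "the rate of grade 2 complications is greater than the reference norm of 30" per cent, with p = 0.048.
- **Grade 3:** if "2 or more patients present with grade 3 toxicity", the plan draws the same kind of conclusion against a norm of 2%, with p = 0.059.

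Either trigger convenes the DSMB, which decides whether the study continues. Neither stops the study automatically.

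The same section sets significance at p below 0.05 and says that reported p-values are two-sided. For the safety endpoints it specifies only that the highest grade of a repeated event counts. The general descriptive paragraph adds point estimates, numbers and percentages. The sample size section plans 70 patients. No toxicity threshold is stated after the 20th patient.

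**The concern.** The purpose clause promises reassurance, but the rule works in the other direction: it looks for evidence of an excess. If neither trigger fires, the only support for saying that toxicity is as expected is a failure to reject in 20 patients. The plan gives no excess worth detecting, no detection probability and no confidence bound. For the primary endpoint, by contrast, it states the null, the alternative, the error rate and the power.

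What is at stake is how the DSMB and later readers interpret a quiet look, and whether a moderate excess would prompt a review while the other 50 patients (70 − 20) are being recruited and treated.

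A separate wording problem concerns grade 3: the plan says an excess can be stated on a p-value above its own significance level.

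**Working it through.** **Inputs from the plan:** n = 20; triggers of 10 or more (grade 2) and 2 or more (grade 3); norms of 30% and 2%; stated p-values of 0.048 and 0.059; significance level 0.05; 70 patients planned.

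**Assumed inputs:** the true rates used as alternatives, because the plan gives only the norms. A range is shown.

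**1. The plan's own figures.** With X binomial (n = 20):

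- Grade 2: P(X ≥ 10 | 0.30) = 0.0480. This matches.
- Grade 3: P(X ≥ 2 | 0.02) = 1 − 0.98^20 − 20 × 0.02 × 0.98^19 = 1 − 0.6676 − 0.2725 = 0.0599. The plan's 0.059 is this value truncated.

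Both are one-sided exact tails. Two-sided exact values would be 0.083 (minimum likelihood) or 0.096 (doubled) for grade 2, and 0.060 or 0.120 for grade 3.

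**2. Probability that a trigger misses a true excess.** For grade 3 this is P(X ≤ 1 | p) = (1 − p)^20 + 20p(1 − p)^19. At p = 0.10 it is 0.1216 + 0.2702 = 0.392. For grade 2 it is P(X ≤ 9 | p).

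| Grade 3 true rate | Missed | Grade 2 true rate | Missed |
|---|---|---|---|
| 5% | 74% | 40% | 76% |
| 10% | 39% | 50% | 41% |
| 20% | 7% | 60% | 13% |

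Detection reaches 80% only at a true rate of about 14% for grade 3 and about 57% for grade 2.

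**3. What a silent look leaves open.** These are exact (Clopper-Pearson) one-sided 95% upper bounds:

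- 0/20: 1 − 0.05^(1/20) = 13.9%
- 1/20: 21.6%
- 9/20: 65%

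The first two compare with a norm of 2%, the third with 30%. This step needs no assumed alternative.

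**4. How much silence tells us.** A silent grade 3 trigger has probability 0.940 at a true 2% and 0.392 at a true 10%. The ratio is 0.940 / 0.392 = 2.4.

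**5. Whether the cut-off is to blame.** Requiring 3 or more of 20 for grade 3 would give p = 0.007, but would miss a true 10% in 68% of trials instead of 39%.

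**6. Adding one cumulative look at 40.** The smallest cut-offs with a one-sided exact p below 0.05 are 18/40 for grade 2 (p = 0.032; 17/40 gives 0.063) and 3/40 for grade 3 (p = 0.046; 2/40 gives 0.190). Detection at either look is 1 − Σ P(X₁ = x) P(X₂ ≤ c − 1 − x). Here X₁ and X₂ are the counts in the first and second 20 patients, c is the cut-off at 40, and the sum runs over values of x that do not trigger at 20.

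| | Look at 20 only | Looks at 20 and 40 |
|---|---|---|
| Grade 2, true 50%: detected | 59% | 82% |
| Grade 3, true 10%: detected | 61% | 81% |
| Grade 2, true 30%: false alert | 4.8% | 6.5% |
| Grade 3, true 2%: false alert | 6.0% | 8.1% |

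**7. Limit at full recruitment.** With 0/70 grade 3 events the upper bound is 1 − 0.05^(1/70) = 4.2%, still above 2%.

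**The case against.** The case for leaving the look alone has real force.

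- **It is an alert.** A trigger leads to a DSMB meeting with full discretion, so a cut-off slightly above 5% is a reasonable choice and the more sensitive one (step 5). This stands.
- **Toxicity is followed elsewhere.** The schedule of assessments records it weekly during radiotherapy, one month after radiotherapy (M1) and at the six-monthly visits. It is a secondary endpoint for the whole cohort, and treatment plans are reviewed centrally. This also stands, but none of it supplies a threshold, a detection probability or a bound.
- **Large excesses are caught.** The look detects a 20% grade 3 rate 93% of the time and a 60% grade 2 rate 87% of the time. True, and it is what the plan should say.

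A reader might also draw stronger conclusions that the documents do not support:

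- *The look rests on non-significant tests, and that is why it misses excesses.* On the one-sided scale the plan actually used, grade 2 is below 0.05; only grade 3 is above it. The misses come from 20 patients and, for grade 3, a low event rate.
- *A silent look is no evidence of safety.* The ratio of 2.4 in step 4 is weak evidence, but not none.
- *The trial intends to report silence as confirmed safety.* The plan draws an explicit inference only when a trigger fires. The reassurance is confined to the purpose clause.

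**Conclusion.** The concern holds in a limited form. This is the only formal toxicity trigger in the documents, and it can flag only large excesses. It therefore cannot do what its purpose clause says. At a true grade 3 rate of 10% it stays silent in 39% of trials, and at a true grade 2 rate of 50% in 41%. Those rates are assumptions; over the ranges tabulated, the miss probability runs from 74% to 7% (grade 3) and from 76% to 13% (grade 2). The 13.9% upper bound for 0/20 depends on no such choice.

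The grade 3 threshold is acceptable as an alert. Stating that the grade 3 rate exceeds 2% on p = 0.059 is not supported at the plan's own 0.05 level.

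It would be wrong to infer that monitoring through to 70 patients would close the gap in patient protection. Once M1 data exist on all 70, everyone has finished radiotherapy, so a look at that point serves reporting only.

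**What to change.** 1. **Wording.** Replace the purpose clause with *to detect a large excess of toxicity*. Give the detection probabilities beside the thresholds (grade 2: 59% at a true 50%; grade 3: 61% at a true 10%), with the alternatives marked as assumptions. Describe the grade 3 threshold as an alert for DSMB review, not as a statement of excess. Label both p-values as one-sided exact, since the section says reported p-values are two-sided.
2. **Reporting.** At the look and in the final analysis, give the grade 2 and grade 3 rates with exact one-sided 95% upper bounds beside the 30% and 2% norms, and limit any conclusion to those bounds. Note that even 0/70 leaves 4.2%, so this trial cannot confirm the 2% norm.
3. **Optional.** Apply the same alert to cumulative M1 data at 40 patients (18/40 for grade 2, 3/40 for grade 3). The DSMB keeps its discretion.

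Items 1 and 2 cost wording and a few exact bounds, and the safety conclusion becomes more guarded. Item 3 uses data already collected. Its price is more false DSMB alerts at the norm rates: 6.5% instead of 4.8% for grade 2, and 8.1% instead of 6.0% for grade 3. None of the three needs extra patients or visits.

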	
 4) Previous radical treatment to the prostate (radiotherapy or surgery) 5) PSA increase of at least 3 assays in the same laboratory over the last 12 months. 6) 1-5 pelvic lymph node metastases detected with 18FCH-PET. A relapse in the dressing prostatectomy is associated possible. 7) Upper limit of lymph node metastases: aortic bifurcation 8) Respect of dosimetry constraints to organs at risk 9) Treatment with hormone therapy may be started before inclusion, to a maximum of three months prior to Day 1 of radiotherapy. This hormone will necessarily be preceded by a free interval treatment of at least 6 months since the last injection, by adding the duration of action of this predictable injection (1, 3 or 6 months) 10) Patient affiliated to a social security scheme 11) Patient Information and written informed consent form signed
NON-INCLUSION CRITERIA	
 1) Bone or visceral metastatic relapse associated 2) Para-aortic nodal relapse (the upper limit is tolerated aortic bifurcation) 3) More than 5 lymph node metastases 4) Proof of metastases at initial diagnosis 5) Evidence of distant metastases in the pelvic lymph nodes or outside the prostate bed prior pelvic lymph nodes irradiation. Irradiation of the bed of the prostate is not an exclusion criterion, but the junction between prior irradiation bed prostatectomy and radiation field pelvic lymph nodes should be examined carefully 6) Castration resistance defined by clinical or biochemical progression despite a combined androgen blockade 7) Known contraindications to pelvic irradiation (eg, chronic inflammatory bowel disease, ...) 8) Known contraindications to hormone therapy, according to standard recommendations in force 9) Serious hypertension not controlled by appropriate treatment 10) Other concomitant cancer or history of cancer (within 5 years prior to study entry), except basal cell or squamous cell carcinomas of the skin. 11) Patient with a psychological, familial, sociological or geographical potentially hampering compliance with the study protocol and follow-up schedule 12) Patient already included in another interventional study involving the approval of a cpp during his screening for the study Oligopelvis 13) Private person of liberty or major trust

E) INVESTIGATIONAL TREATMENT DESCRIPTION

Experimental procedure

- **Radiation therapy**

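### The 20-patient toxicity look has no baseline CTCAE grade, so earlier-treatment and hormonal symptoms could be counted as irradiation toxicity

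*Combined protocol and SAP*

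**What the plan says.** Section F, under the statistical criteria for stopping the study, sets out the look: "An analysis of acute toxicity persisting at one month after radiotherapy will be performed after the inclusion of the 20th patient". Its purpose is "to ensure that the toxicity of the irradiation protocol is not higher than expected".

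There are two triggers:
- Grade 2: "If, among the first 20 patients, 10 or more patients present with grade 2 toxicity", the plan concludes that "the rate of grade 2 complications is greater than the reference norm of 30" per cent (p = 0.048).
- Grade 3: "If, among the first 20 patients, 2 or more patients present with grade 3 toxicity", it concludes the same against a norm of 2% (p = 0.059).

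In either case the DSMB meets and decides whether the study continues. No source is given for the two norms. No organ class, attribution rule or change from baseline is attached to the count.

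The schedule of assessments in section G has one acute toxicity row covering hormone therapy and radiotherapy together, graded by CTCAE v4.0. It is marked weekly during radiotherapy and at M1, one month after its end. The late toxicity row is marked in follow-up. Neither row is marked at inclusion. Inclusion does have physical examination, prior history, blood pressure, and the QLQ-C30 and QLQ-PR25.

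Inclusion criterion 4 requires earlier radical prostate radiotherapy or surgery. Footnote (c) of the schedule gives six months of hormone therapy, starting between three months before radiotherapy and its first day. Secondary objective d) reports acute and late toxicity, with emphasis on gastrointestinal events.

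**The concern.** The stated target is the toxicity of the irradiation. What is counted is persisting acute toxicity in pretreated men on combined treatment. Earlier surgery or radiotherapy can leave urinary, bowel or sexual symptoms, and hormone therapy has effects of its own. With no grade taken before radiotherapy, no scheduled CTCAE record shows whether a grade 2 symptom at M1 is new, worse or unchanged.

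Two things are at stake. A trigger could fire although irradiation toxicity is at its norm, or could fire in a way the DSMB finds hard to interpret. And in a single-arm trial, secondary objective d) loses the main means of telling new symptoms from old ones. A baseline grade cannot be reliably recovered afterwards.

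**Working it through.** **Inputs from the documents.** n = 20; thresholds 10 (grade 2) and 2 (grade 3); norms 30% and 2% (section F).

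**Reproducing the plan's figures.** Both are exact one-sided binomial tails.
- Grade 2: P(X ≥ 10 | n = 20, p = 0.30) = 0.04796, stated as 0.048.
- Grade 3: P(X ≥ 2 | n = 20, p = 0.02) = 1 − 0.98^20 − 20 × 0.02 × 0.98^19 = 1 − 0.6676 − 0.2725 = 0.0599, stated as 0.059 (truncated).

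These are false-alarm probabilities for irradiation only if the counted events are of the same kind as those behind the norms.

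**Is hormone therapy still active at M1?** Section G gives 6 to 7 weeks of radiotherapy (1.4 to 1.6 months), and M1 is one month later. With hormone therapy starting 0 to 3 months before radiotherapy, M1 falls between 0 + 1.4 + 1 = 2.4 and 3 + 1.6 + 1 = 5.6 months after its start, inside a six-month course. Section E also allows 15 days either side of three months, which extends the upper end to 3.5 + 1.6 + 1 = 6.1 months. So M1 generally, but not always, falls within the course.

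**Effect of background events (illustration).** The documents give no background rate, so b is assumed. Suppose irradiation toxicity is exactly at the norm p0, the norm excludes background events, and background is independent of irradiation toxicity. The counted rate is then p = 1 − (1 − p0)(1 − b).

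| Trigger | Assumed b | Counted rate p | P(trigger fires) |
|---|---|---|---|
| Grade 2 | 0 | 0.300 | 0.048 |
| Grade 2 | 5% | 0.335 | 0.095 |
| Grade 2 | 10% | 0.370 | 0.165 |
| Grade 2 | 20% | 0.440 | 0.374 |
| Grade 3 | 0 | 0.0200 | 0.060 |
| Grade 3 | 1% | 0.0298 | 0.119 |
| Grade 3 | 2% | 0.0396 | 0.187 |
| Grade 3 | 5% | 0.0690 | 0.406 |

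For example, grade 3 with b = 2% gives p = 1 − 0.98 × 0.98 = 0.0396. The grade 3 trigger is the more sensitive because two patients suffice.

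**Relaxing the assumptions.**
- Full overlap: if the patients with background symptoms are also those with irradiation toxicity, the counted rate stays at p0 for any b up to p0. The probabilities stay at 4.8% and 6.0%.
- Norms that already include hormonal effects: that part of the background is inside the 30% and 2%, and adds little or nothing.

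**Would an inclusion grade precede treatment?** Inclusion is at most two months before radiotherapy. Criterion 9 lets hormone therapy start before inclusion. The radiotherapy text in section E starts radiotherapy three months ± 15 days after the first injection, which puts inclusion at least 2.5 − 2 = 0.5 months after that injection. The hormone therapy text in section E, and footnote (c), also allow a start on the first day of radiotherapy, which is after inclusion. These passages must be reconciled. Either way, an inclusion grade precedes radiotherapy but does not always precede hormone therapy.

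**The case against.** The strongest case against has four parts.

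- **The count is narrower than all grade 2 or 3 toxicity.** It is acute toxicity persisting after radiotherapy, and a stable old symptom is not that on an ordinary reading. This stands as a limit on the claim: such symptoms could be counted, not that they are. But no rule says they are excluded, and centres have no baseline grade with which to apply one uniformly.
- **The DSMB has other material.** Prior history, examination and quality of life at inclusion, and weekly grades during radiotherapy, all help attribution. A reader might infer that new injury cannot be separated from old symptoms at all; the documents do not support that. What stands is that none of these is a CTCAE grade taken before radiotherapy.
- **A crossed trigger stops nothing.** A reader might infer that the trial could be wrongly halted. The text only convenes the DSMB, and an over-inclusive count errs towards caution. Counting toxicity of the combination is also defensible, since the combination is the treatment studied. This stands, and it limits the severity.
- **The inflation figures rest on assumed rates, independence and irradiation-only norms.** This stands, so they are an illustration and not an estimate of the trial's false-alarm rate.

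The available document also appears condensed: it cites a section 8.5.1 that it does not contain. An attribution rule may exist elsewhere.

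**Conclusion.** The point holds in a limited form. The triggers have no change-from-baseline condition and the schedule has no CTCAE grade before radiotherapy. Earlier-treatment and hormonal symptoms could therefore enter both the DSMB count and the results for secondary objective d). The consequence is a possible false or hard-to-interpret alarm and a less interpretable safety result, not a forced stop.

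The size is uncertain. Under independence, and with norms free of background events, an assumed 10% grade 2 background takes the firing probability from 4.8% to 17%, and an assumed 2% grade 3 background takes it from 6.0% to 19%. With full overlap, or norms that already include hormonal effects, there is little or no inflation. It would go too far to conclude that the 10-of-20 and 2-of-20 rules are miscalibrated: their arithmetic reproduces, and whether the norms match the count cannot be judged without their source. The case for acting rests mainly on the low cost of a baseline grade and on its not being recoverable later.

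**What to change.** 1. Add CTCAE v4.0 grading to the existing inclusion visit, label it a pre-radiotherapy baseline, and record whether hormone therapy has already started.
2. In the DSMB report and in the acute and late toxicity tables, show events whose grade is worse than that patient's baseline alongside the all-event count. Show gastrointestinal and genitourinary events separately from other (hormonal) events. The split is needed because hormonal effects that emerge after inclusion would still count as worsened.
3. State the source of the 30% and 2% norms and what they count. Keep the all-event trigger as written unless that source shows that the norms refer to new or worsened events. Narrowing the count against unchanged norms could make the triggers too insensitive.

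The cost is one more CRF page at a planned visit and a few lines in the SAP. The limitation is that, for patients already on hormone therapy at inclusion, the baseline may include early hormonal effects. It remains a pre-radiotherapy grade, which is what an irradiation check needs.
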